7.2.5 Sponsor Responsibility for Reporting Adverse Events

The site investigator must report any expected Serious Adverse Event (SAE-E) or unexpected Serious Adverse Event (SAE-U) that occurs during the treatment period starting at the time the consent is signed, through 90 days following cessation of treatment, or 30 days following cessation of treatment if the participant initiates new anticancer therapy, whichever is earlier, regardless of whether it is attributable to the study drug. Events must be reported to the Yale Project Manager and Sponsor PI within 24 hours of becoming aware of such events.

Sites are responsible for reporting to their IRB per local policy. All events will be forwarded by the Yale Project Manager to Merck as required following the method and timeline outlined below.

All SAEs should be entered into the EDC system within 24 hours of the site becoming aware of the event.

Any delayed serious adverse event (occurring after the 90-day period) that may reasonably be considered related to the treatment(s) described in the protocol or to the study must be reported, and no time limit applies to such adverse events. For each event, the investigator shall complete the SAE reporting form. SAEs will be followed until resolution or until clinically relevant improvement or stabilization.

The study site should send the SAE form to the Yale Project Manager and Sponsor PI as soon as possible so that the tracking procedure can begin immediately upon receipt of the information. Once the Yale Project Manager and Sponsor PI are informed of an SAE with preliminary information obtained, the study site will be instructed to update the SAE form with additional information, as per the following guidelines.

If all information is not known at the time of the incident, an initial report should still be made. In the event there is a question as to whether the event is serious, the information should be forwarded to the Yale Project Manager and Sponsor PI for review. Each Site PI is responsible for following up on completion of the SAE form. The Investigator will submit substantiating data in hard copy form, such as diagnostic test reports and progress notes, to the Yale Project Manager and Sponsor PI. In the case of fatality, autopsy reports will be furnished to the Yale Project Manager and Sponsor PI as soon as available. During the initial communication, the Yale Project Manager will require the following information about the patient and the reported SAE:

- patient identification including patient number, initials, and date of birth
- date of first dose of study drugs and details of administration, including study drug names (including labeled strength and manufacturer), lot number, expiration date, and dose;
- date of last dose of study drugs (i.e., prior to onset of SAE) and details of administration, including study drug names (including labeled strength and manufacturer), lot number, expiration date, and dose)

- medical diagnosis of the event in standard medical terminology (if a medical diagnosis cannot be determined, a description of each sign or symptom characterizing the event)
- date of onset of the AE
- date of resolution of the AE (or confirmation ongoing)
- severity of the AE
- assessment of the attribution of the AE to the study drug
- reason AE is considered serious
- whether the AE is expected
- action taken in treating the AE and/or change in study drug administration or dose (including concomitant medications or therapies administered, whether hospitalization or prolongation of hospitalization was required, diagnostic procedures performed, and whether the patient was discontinued from the study); all concomitant medications (including doses, routes, regimens, and indications)
- pertinent clinical laboratory testing data
- medical history

The Sponsor PI will review each SAE report and evaluate the relationship of the adverse reaction to the study drug and to the underlying disease. Based on the Investigator's and Sponsor PI assessment of the adverse experience, a decision will be made concerning further actions. The primary consideration governing further action is whether new findings affect the safety of patients participating in the clinical study. If the discovery of a new adverse experience related to the study drug raises concern over the safety of continued administration of study drug, the Sponsor PI will take immediate steps to notify the regulatory authorities.

7.2.7 Reporting to the IRB

Sites are responsible for reporting to their IRB per local policy.

8.0 STATISTICAL ANALYSIS PLAN

8.1 Statistical Analysis Plan Summary

Key elements of the statistical analysis plan are summarized here.

Study Design Overview	A non-randomized phase 2, Simon's 2-stage designed trial to evaluate intracranial response to pembrolizumab and lenvatinib in anti-PD-1/PD-L1 experienced patients with untreated brain metastases evaluated in 2 cohorts: 1) melanoma and 2) RCC
Treatment Assignment	Approximately 62 participants will be allocated between 2 groups: cohort 1/melanoma (PD-1/PD-L1-experienced) will have 30 participants, and cohort 2/RCC (PD-1/PD-L1 experienced) will have 32 participants.
Analysis Populations	Efficacy: Intention to Treat (ITT) Safety: All Participants as Treated (APaT)
Primary Endpoints	Best brain metastasis response per mRECIST 1.1, up to 5 previously untreated or progressing intracranial tumors will be followed.
Key Secondary Endpoints	1) Best overall response rates per RECIST 1.1 2) PFS and OS 3) Duration of intracranial response 4) Adverse events

Statistical Methods for Secondary Endpoints	
1) A Chi-squared analysis and 95% confidence interval will be employed to evaluate the overall response rate.
 
2) PFS and OS will be evaluated using the Kaplan-Meier method.
 
3) Duration of intracranial response will be evaluated by the Kaplan-Meier method.
 
4) Adverse events will be assessed tabulated by frequency with descriptive statistics such as grade, attribution, and type.

---------------------------------------------	-------------------------------------------------------------------------------------------------------------------------------------------------------------------------------------------------------------------------------------------------------------------------------------------------------------------------------------------------------------------------------------------------------------------------

8.2 Sample Size Considerations

Cohort 1: Melanoma

A second-line immunotherapy option for patients who have progressed on anti-PD-1/PD-L1 may be ipilimumab, which has an estimated response rate of approximately 10% in the second-line setting in extracerebral melanoma (Bowyer et al., 2016; Long GV, 2016). An immune therapy regimen which is modestly active in patients with melanoma brain metastases whose disease had progressed on PD-1/PD-L1 inhibitors would be expected to have a brain metastasis response rate of an estimated 5%, as this represents a sicker patient population. Pembrolizumab combined with lenvatinib will be considered worthy of further study in patients with untreated brain metastases who are PD-1/PD-L1 inhibitor-experienced if the true brain response rate is 20%. Simon's two-stage design will be used, with 80% power and a one-sided level of significance equal to 0.05. In the first stage, 13 patients will be accrued. If there are 0 responses in these 13 patients, this cohort will be stopped for futility. Otherwise, 14 additional patients will be accrued for a total of 27 patients. The null hypothesis will be rejected if 4 or more responses are observed in 27 patients. Due to an anticipated drop-out of 10% either due to being unevaluable in the brain due to loss to follow-up or death due to extracranial disease prior to initial response evaluation, we anticipate enrolling 30 patients for at least 27 evaluable.

Cohort 2: Renal cell carcinoma

Frontline standard of care therapies for metastatic renal cell carcinoma (RCC) are variable and may include anti-PD-1/PD-L1 +/- anti-CTLA-4, pembrolizumab + axitinib, or an antiangiogenic TKI. There are very limited data on the efficacy of second-line systemic therapy for untreated brain metastases in patients with RCC. Nivolumab as a second-line immunotherapy option for patients with untreated RCC brain metastases who have progressed on antiangiogenic or cytokine therapy has an intracranial response rate of 12% (Flippot et al., 2019). This is the same as the objective response rate reported for sunitinib in patients with RCC brain metastases (Gore et al., 2011). Checkpoint inhibitors combined with antiangiogenic therapies such as pembrolizumab plus

lenvatinib and pembrolizumab plus bevacizumab have demonstrated activity against RCC in the second-line setting, with ORR of 51% and 61%, respectively, in small early phase trials (Dudek et al., 2020; Lee et al., 2020; Taylor et al., 2020), but there is no data for these combinations in RCC brain metastases which represents a sicker patient population. Therefore, we propose that pembrolizumab combined with lenvatinib will be considered worthy of further study in RCC patients with untreated brain metastases who are PD-1/PD-L1 inhibitor-experienced if the true brain response rate is 30%. Simon's two-stage design will be used, with 80% power and a type I error rate of 0.05. In the first stage, 18 patients will be accrued. If there are 2 or fewer responses in these 18 patients, this cohort will be stopped for futility. Otherwise, 11 additional patients will be accrued for a total of 29 patients. The null hypothesis will be rejected if 7 or more responses are observed in 29 patients. Conservatively estimating for a 10% drop out rate accounting for patients who may be unevaluable due to inability to reach the first intracranial assessment scan, an additional 3 patients may be enrolled if needed, for a total of 32 patients.

8.3 Statistical Analysis Plan

This section outlines the statistical analysis strategy and procedures for the study. If after the study has begun, changes are made to primary and/or key secondary hypotheses, or the statistical methods related to those hypotheses, then the protocol will be amended (consistent with ICH Guideline E9).

All baseline patient demographics and clinical characteristics will be summarized by mean/standard deviations and count/frequency for continuous and categorical variables respectively. All analyses will be completed as intent to treat.

Intracranial and Objective Response Rate

The primary endpoint is the best brain metastasis response rate of pembrolizumab in combination with lenvatinib. For the primary objective, the proportion of patients that experienced an intracranial response in each cohort will be estimated with corresponding 95% confidence interval.

The combination will be deemed worthy of further study as outlined in the Simon 2-stage designs in Section 8.2.

For objective response rate, the proportion of patients experience an objective response in each cohort will be estimated with corresponding 95% confidence interval.

PFS and OS

The non-parametric Kaplan-Meier method will be used to estimate median survival, along with survival at 1 year and 2 years.

Participants without documented event at the time of analysis will be censored at the date of last clinical evaluation for each outcome.

Duration of Intracranial Response Analysis

Duration of intracranial response will be evaluated by the Kaplan-Meier method. Intracranial responses will be analyzed separately from extracranial responses. If the patient has SD/PR/CR in the brain but PD in the body, then the patient will still be considered to have an ongoing intracranial response.

Statistical Methods for Safety Analyses

AEs will be coded using the standard Medical Dictionary for Regulatory Activities (MedDRA) and grouped system organ class. AEs will be graded by the investigator according to the NCI CTCAE, v5.0.

All subjects will be included in the safety analysis. Incidence tables will be generated to summarize incidence of patients reporting at least one episode of each specific adverse event, incidence of adverse events causing withdrawals and incidence of serious adverse events. Listing of adverse events by patients will include the time to onset, the duration of each event, the severity of each event, and the relationship of the event to study therapy, whether it was a serious event, and whether it caused withdrawal.

Exploratory Objectives

Biomarker Studies

Immunohistochemical evaluation of baseline tumor PD-L1 staining, TIL populations, and other immune and angiogenic factors that may predict tumor sensitivity to this drug combination will be compared between non-responders (SD and PD) versus responders (PR and CR) using a mixed methods approach, that adjusts for repeated measures over time and response as defined above. If there are differences by time, pairwise contrasts will be utilized to assess for specific differences at various time points, adjusting for multiple comparisons using the Tukey method.

For patients who have on-treatment tumor samples, comparison will be made to pre-treatment tissue for PD-L1 staining, TIL populations, and other immune and angiogenic factors that may predict tumor sensitivity. Differences in these markers by response will be assessed using two-sample t-test.

Blood samples collected before and on treatment will be analyzed for cytokines and by flow cytometry. Data will be analyzed by a repeated measures ANOVA and adjusted for multiple comparisons via Tukey method.

TIL will be extracted from resected pre-treatment specimens and subjected to immunophenotyping studies to characterize T and B cells using single-cell RNA-sequencing. Data will be analyzed by a repeated measures ANOVA and adjusted for multiple comparisons via Tukey method.

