4.2 Rationale

4.2.1 Rationale for the Trial and Selected Population

Pembrolizumab Rationale:

We previously demonstrated the activity and safety of pembrolizumab in a phase 2 trial for patients with untreated melanoma brain metastases whose lesions were larger than 0.5 cm but less than 2 cm in diameter and did not require corticosteroids for symptom control (Goldberg et al., 2016; Kluger et al., 2019). Most patients had been heavily pre-treated. The brain metastasis response rate was 26%, median OS was 17 months, and 48% of patients were still alive after 2 years (Kluger et al., 2019). Although nivolumab and ipilimumab in combination yielded superior brain metastasis response rates, in excess of 40%, the toxicity of the combination was higher, as seen in patients with extracerebral disease (G. V. Long et al., 2018; Tawbi et al., 2018). Of note, the pembrolizumab monotherapy trial and the two studies of ipilimumab and nivolumab demonstrated consistent concordance between intracranial and extracranial responses.

Immune checkpoint inhibitors are a standard of care therapy for advanced RCC however these studies excluded patients with untreated brain metastases (Motzer, Escudier, et al., 2015; Motzer et al., 2018). The management of brain metastases from RCC remains a therapeutic challenge. Flippot et al. conducted the first prospective study of nivolumab in patients with RCC brain metastases who had progressed on at least one prior treatment with an antiangiogenic agent (Flippot et al., 2019). Single agent nivolumab had limited efficacy against RCC brain metastases with an intracranial response rate of 12% which was about half that of the extracranial response rate. The addition of antiangiogenic therapies to anti-PD-1 in this setting may improve the anti-tumor immune response and increase tumor sensitivity to anti-PD-1 however this has not been studied prospectively in this population.

Lenvatinib Rationale:

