4.2.3 Rationale for Endpoints

4.2.3.1 Efficacy Endpoints

Primary endpoint:

Best brain metastasis response rate (BMRR), defined as PR and CR per modified RECIST 1.1.

Secondary endpoints:

Best overall objective response rate, defined as PR and CR per RECIST 1.1.

PFS, defined as the time from start of study drug administration to the date of the first documentation of disease progression or death from any cause, whichever occurs first.

OS, defined as the time from start of study drug administration to date of death from any cause.

Duration of brain metastasis response, defined as the time from response to the time of the first documentation of intracranial disease progression.

Safety and rate of adverse events, particularly neurologic adverse effects, which include worsening of edema and development of radiation necrosis.

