5.3 Treatment Allocation

This is a phase 2, non-randomized study with 2 cohorts of anti-PD-1/PD-L1 experienced patients with untreated brain metastases: 1) melanoma and 2) RCC. After establishing eligibility, patients will undergo fresh biopsy of a metastatic site, if feasible. The biopsy requirement can be waived

if there is not an easily accessible site to biopsy or if a biopsy is determined to be unfeasible by the treating physician after discussion with the study PI. Archived metastatic tumor tissue, including prior CNS tumor tissue, should also be submitted, if available. The tumor tissue will be studied retrospectively for PD-L1 expression, TIL characteristics, and other immune and angiogenic markers that may predict sensitivity to this drug combination. Pembrolizumab 200mg IV every 3 weeks will be administered in combination with lenvatinib 20 mg PO daily.

MRI of the brain will be obtained after 6 weeks of therapy for initial assessment of efficacy by mRECIST, and a confirmation scan will be performed at 12 weeks. CT body scans (and/or MRI or PET CT as clinically indicated) will also be done at these times to evaluate for extracranial response by RECIST. The next MRI brain or body imaging will be done every 12 weeks thereafter. Patients will continue on study until they have overall disease progression in either their clinically evaluable CNS lesions or in their systemic metastases, toxicities that preclude continuing the study drug, withdrawal from study, termination of study, or death. Dose reductions for immune-related toxicities will not be allowed.

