Pregnancy Test – Urine or Serum β-HCG	X	X	X	X	X	X	X	X	X	X	X			Performed within 10 days of C1D1 and prior to all subsequent scheduled visits. Every effort should be made to collect samples at the same time of day. LDH is only required at screening. Urine protein ≥2 requires 24-hour urine collection and D15 re-evaluation per Section 5.2.2.7. Pregnancy test for WOCP to be done within 72 hours days of C1D1.
PT/INR and aPTT	X													
CBC with Differential	X		X	X	X	X	X	X	X	X	X			
Comprehensive Serum Chemistry Panel	X		X	X	X	X	X	X	X	X	X			
Urinalysis	X		X	X	X	X	X	X	X	X	X			
T3, FT4 and TSH	X		X	X	X	X	X	X	X	X	X			
Efficacy Measurements														
Tumor Imaging (MRI brain ^e and CT Chest, Abdomen, Pelvis)	X		X		X				X	X		X	X	Prior scans performed within the screening period but before signing informed consent may be

														used. All imaging visits have a scheduling window of ± 7 d. Intracranial disease progression will be assessed by mRECIST 1.1. Extracranial disease will be assessed by RECIST 1.1. For participants who DC for reasons other than PD, imaging should be performed Q12W. Imaging at EOT is not required if the previous tumor imaging assessment was within 4 weeks prior to the EOT visit. Imaging of any anatomy that shows disease either at screening or in subsequent evaluations will be required and should be submitted.
Tumor Biopsies/Archival Tissue Collection/Correlative Studies														
Archival or Newly Obtained Tissue Collection	X													New tissue will be collected if the patient has a biopsy or resection for any reason while on study; a new consent will be obtained from the subject for use of part of the collected tissue for research.
Correlative Studies Blood Collection ^f		X	X	X			X			X				

a. Participants who continue treatment with lenvatinib beyond approximately 2 years (only if they experience clinical benefit until unacceptable toxicity or disease progression and upon Sponsor consultation and approval) will follow the same SOA except that thyroid labs beyond approximately 2 years will be performed per SOC or as clinically indicated.

b. If EOT visit occurs ~30 days from last dose of study treatment, a 30-day safety follow-up visit is not required. In this situation, all procedures required at the 30-day Safety Visit and EOT are performed once and entered into the EOT visit only. End of treatment will be defined as the date when the participant discontinues all trial treatments.

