7.1.2.9.2 Tumor Imaging During the Study

The first on-study imaging assessment for best BMRR by brain MRI should be performed at 6 weeks (42 days ± 7 days) from the date first study dose. Response assessment will be confirmed at 12 weeks. Subsequent tumor imaging should be performed every 12 weeks (84 days ± 7 days) or more frequently if clinically indicated. Imaging timing should follow calendar days and should not be adjusted for delays in cycle starts. Imaging should continue to be performed until disease progression is identified by the Investigator.

Best overall objective response should be confirmed by repeat imaging assessment. Initial best overall response assessment will be done by CT scans (preferred) performed at 6 weeks (42 days \pm 7 days) from the date first study dose. Response assessment will be confirmed at 12 weeks. Subsequent tumor imaging should be performed every 12 weeks (84 days \pm 7 days) or more frequently if clinically indicated. Imaging timing should follow calendar days and should not be adjusted for delays in cycle starts.

Participants who have disease progression may continue on treatment at the discretion of the Investigator and study PI provided they have met the conditions detailed in Sections 5.5.4.

In participants who discontinue study treatment, tumor imaging should be performed at the time of treatment discontinuation (\pm 4 week window). If previous imaging was obtained within 4 weeks prior to the date of discontinuation, then imaging at treatment discontinuation is not mandatory.

In participants who discontinue study treatment without documented disease progression, every effort should be made to continue monitoring their disease status by tumor imaging using the same imaging schedule used while on treatment (every 12 weeks) to monitor disease status until the start of a new anticancer treatment, disease progression, pregnancy, death, withdrawal of consent, or the end of the study, whichever occurs first.

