7.1.5.3.3 Survival Follow-up

Participants who experience confirmed disease progression or start a new anticancer therapy, will move into the Survival Follow-Up Phase and should be contacted by telephone every 12 weeks to assess for survival status until death, withdrawal of consent, or the end of the trial, whichever occurs first.

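### Section 8.3 keeps patients with extracranial progression in intracranial response, but the protocol contradicts itself on whether their brain MRI continues, and no censoring date is tied to a brain scan

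*Combined protocol and SAP*

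**What the plan says.** **Endpoint.** Section 4.2.3.1 defines duration of brain metastasis response as "the time from response to the time of the first documentation of intracranial disease progression". Section 8.3 analyses it by Kaplan-Meier, separately from extracranial response. When the brain is stable or better and the body has progressed, section 8.3 says that "the patient will still be considered to have an ongoing intracranial response".

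**Censoring.** The only rule in section 8.3 stands under the PFS and OS heading. It censors patients without an event at their last clinical evaluation. The paragraph on intracranial duration gives no rule of its own.

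**Text that points to imaging ending at progression.**
- Section 5.3: "Patients will continue on study until they have overall disease progression in either their clinically evaluable CNS lesions or in their systemic metastases".
- Section 7.1.2.9.2: "Imaging should continue to be performed until disease progression is identified by the Investigator". The same section asks for further 12-weekly imaging in patients who stop treatment without documented progression.
- Section 6.1, note to the imaging row: "For participants who DC for reasons other than PD, imaging should be performed Q12W". Section 7.1.5.3.2 limits the imaging follow-up phase in the same way.
- Section 7.1.5.3.3: after confirmed progression or new therapy, patients "should be contacted by telephone every 12 weeks to assess for survival status".

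**Text that points to imaging continuing.**
- The tumor imaging row of the flow chart, which covers brain MRI, has a mark in the Survival Follow-Up column. So does the directed physical examination row.
- Flow chart note e sets brain MRI at weeks 6 and 12, every 12 weeks after that, and every 24 weeks after week 102. It names no stop at extracranial progression.

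**Confirmation.** Section 7.1.2.9.4 requires every brain response to be confirmed at 12 weeks.

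**The concern.** The section 8.3 rule can be applied only if someone keeps looking at the brain after the body has progressed. A site that follows the text would stop scanning such a patient, and a site that follows the flow chart would not. The analyst would then have a mixture of observed and unobserved brain follow-up, with no instruction on where the unobserved part ends.

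Two things are at stake. First, the reported intracranial duration could be too long. Section 4.2.1 says that earlier melanoma brain metastasis trials "demonstrated consistent concordance between intracranial and extracranial responses". If progression times are also linked, censoring at extracranial progression removes the patients whose brain disease is nearest to progressing. Carrying the response forward as ongoing credits time with no scan behind it. Second, a patient with a brain response and extracranial progression at week 6 could miss the week-12 MRI on which confirmation of the primary endpoint depends.

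**Working it through.** **1. One patient, two readings.** Take a confirmed brain responder with extracranial-only progression who stops treatment.

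| Question | Text (5.3, 7.1.2.9.2, 7.1.5.3.2, 7.1.5.3.3, note in 6.1) | Flow chart row and note e |
|---|---|---|
| Brain MRI afterwards? | Not required; telephone contact | Marked; every 12 weeks |
| Intracranial progression observable? | Only by an unscheduled scan | Yes |
| Status under 8.3 | Ongoing, unobserved | Ongoing, observed |
| Censoring date | Not tied to a scan | Not tied to a scan |

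**2. Illustration for duration.** The documents give no intracranial duration for this regimen. Two RCC figures are borrowed from section 4.2.1, as assumptions only: a median response duration of 9.9 months as the true brain duration, and a median PFS of 11.7 months as the time to extracranial progression. Both times are taken as exponential and linked by a Gaussian copula. Data cut-off is assumed uniform between 24 and 60 months.

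At correlation 0 the share with extracranial progression first is 9.9 / (9.9 + 11.7) = 0.46. The simulation gives:

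| Correlation | Extracranial first | KM median, censored at extracranial PD | KM median, carried as ongoing to cut-off |
|---|---|---|---|
| 0 | 0.46 | 9.8 | 19.7 |
| 0.3 | 0.45 | 11.1 | 21.7 |
| 0.6 | 0.43 | 12.7 | 23.0 |
| 0.8 | 0.40 | 13.8 | 22.7 |

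With complete MRI follow-up the median is 9.8 to 9.9. With an assumed true median of 6 months, the two strategies give 6.0 to 7.0 and 8.0 to 8.5 months. Censoring therefore does no harm without correlation, and its bias grows with correlation. Carrying forward is biased at every correlation.

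Counting extracranial progression as the end of response gives a low bracket. At correlation 0 the median is 9.9 × 11.7 / (9.9 + 11.7) = 5.4 months.

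**3. Number of responders.** At the target rates, 0.20 × 27 = 5.4 in melanoma and 0.30 × 29 = 8.7 in RCC.

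**4. Confirmation and the primary endpoint.** The plan's power reproduces. Power = Σ over x₁ above the futility bound of Bin(x₁; n₁, p) × P(X₂ ≥ r − x₁), where X₂ is the stage-2 count and r is the number of responses needed. Melanoma (stop at 0 of 13; r = 4 of 27; p = 0.20) gives 0.801. RCC (stop at 2 or fewer of 18; r = 7 of 29; p = 0.30) gives 0.801.

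If a share q of true brain responders lacked the confirming MRI and counted as non-responders, p becomes p(1 − q):

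| q (assumed) | Melanoma power | RCC power |
|---|---|---|
| 5% | 0.765 | 0.750 |
| 10% | 0.724 | 0.691 |
| 20% | 0.629 | 0.552 |

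No value of q can be taken from the documents. Section 2.2 calls patients unevaluable if they do not reach the 6-week scan, so a week-6 responder without a week-12 MRI remains evaluable. Section 8.3 does not say how that patient counts.

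**The case against.** The strongest reply is that brain imaging does not plainly stop.

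- **The flow chart schedules it.** Imaging and examination are marked in Survival Follow-Up, and note e has no stop at extracranial progression. This stands. The finding is a contradiction, and a reader who infers that duration cannot be measured goes too far. Kaplan-Meier uses all follow-up to the last brain MRI.
- **The stop sentence in 7.1.2.9.2 names no site.** It closes the paragraph on brain MRI and may mean intracranial progression. That is a fair reading, but sections 7.1.5.3.2 and 7.1.5.3.3 do not make the distinction.
- **Week-6 responses are not necessarily lost.** A reader might infer that some can never be confirmed. Mandatory discontinuation (5.6) and survival follow-up (7.1.5.3.3) refer to confirmed progression. Section 7.1.2.9.8 describes confirmation at least 4 weeks later, so week 10 or later after a week-6 scan, which fits the week-12 visit. Treatment beyond progression is also allowed at the discretion of the investigator and PI. The gap remains for a patient who stops at once, whose discontinuation scan is waived because of a scan in the prior 4 weeks, and who has no later MRI.
- **The last-clinical-evaluation rule belongs to PFS and OS.** No text says that a telephone call extends a brain response. This stands; the defect is the absence of a rule for intracranial duration.
- **Concordance is about responses, not progression times**, and comes from melanoma trials of other regimens. For RCC, section 4.2.1 reports an intracranial rate about half the extracranial one under nivolumab. Correlation is therefore plausible but not shown.
- **The endpoint is imprecise anyway.** With complete follow-up and a true median of 9.9 months, the 95% sampling range of the KM median is about 2 to 27 months with 5 responders and 3 to 22 with 9. A shift of 2 to 3 months is small beside that, though it is systematic and avoidable.

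**Conclusion.** The concern holds as an unresolved contradiction with a missing censoring rule. Section 8.3 relies on brain scans that the flow chart marks and the text does not secure. Under the text reading, the reported intracranial duration can be biased long.

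The documents do not fix the size. For an assumed true median of 9.9 months the illustration gives 9.8 to 13.8 months with censoring at extracranial progression, and about 20 to 23 if the response is carried forward without MRI. These figures rest on borrowed all-disease RCC medians, exponential times and assumed correlations of 0 to 0.8.

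A reader might also infer a definite loss of power for the primary endpoint. The documents do not support that, because the share of brain responders who would miss confirmation is unknown. The power table shows sensitivity only, and the Simon designs themselves are not in error. The matter should be settled before analysis, but it does not undermine the trial.

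**What to change.** 1. **Section 8.3:** censor intracranial duration at the last evaluable brain MRI, not at the last clinical evaluation or contact. This costs nothing.
2. **Assessment schedule:** reconcile sections 5.3, 6.1 (row, note and note e), 7.1.2.9.2, 7.1.5.3.2 and 7.1.5.3.3. Brain responders, confirmed or awaiting confirmation, whose progression is extracranial only should keep the brain MRI that the flow chart already marks, including the week-12 scan. It would end at intracranial progression, new systemic therapy, brain-directed local therapy or death. This concerns imaging only and leaves treatment decisions as they are.
3. **Sensitivity analysis:** add one analysis that ends the response at discontinuation for extracranial progression, as a low bracket beside the main estimate.

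The cost is protocol wording and a few MRIs. About 5 and 9 responders are expected per cohort, and under the illustration 40 to 46% of them would have extracranial progression first. The reported duration may come out shorter.

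The fix does not remove all the bias, because censoring at new therapy can still be informative. If new therapy is assumed to start 1 month after extracranial progression, at correlation 0.5, the KM median falls only from about 12 to 11.5 months against a true 9.9.
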